### 6 HANDLING OF MISSING VALUES AND OTHER DATA CONVENTIONS

Missing data is expected to be at random and due to device fault or misplaced registration. No data are extracted from questionnaires or physical follow-up by the patients. Missing values will be handled using pairwise deletion, still analysing all cases with the variable of interest.

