The blood samples for the study were drawn preoperatively or within the first 24 hours of surgery (only preoperative data for hsCRP included), and stored in the Persimune Biobank or two other biobanks at Dept. Cardiothoracic Anaesthesiology and Dept. Cardiothoracic Surgery, Rigshospitalet (registered with [name], PhD and [name], respectively). The blood samples from the established biobanks were obtained in relations to research projects on patients undergoing cardiac surgery. When the patients were giving informed consent to participate in the study they were informed about, they were also at the same time giving consent to the blood samples to be obtained for future research (see attached participant information). Blood samples stored in Persimune Biobank from patients undergoing cardiothoracic surgery has continuously been included by MD, PhD [name] and MD [name] at the Dep. of Cardiothoracic Anaesthesiology. The study has been approved by the executive committee of the PERSIMUNE Centre of Excellence.

In this study we will use 850 µL EDTA-plasma in matrix tubes for each patient from a total of ~1000 patients from all three biobanks. All tubes will be transported directly from the respective biobank to the Dep. of Clinical Immunology for suPAR analysis. The tubes will be kept at the Dep. of Clinical Immunology for two days while conducting the analysis and after analysis the tubes including excess biological material will be discarded. Likewise, 850 µL EDTA-plasma in matrix tubes from the ~1000 patients from all three biobanks will be transported directly from the respective biobank to the Dep. of Clinical Biochemistry for hsCRP analysis. They will be kept here for two days while conducting the analysis, and after analysis the tubes including excess biological material will be discarded as well. The analysis will be performed using commercially available analyses (suPARnostic® kit (validated to measure suPAR concentrations between 0.6 and 22 ng/mL) (ViroGates)). HsCRP will be measured by high sensitivity CRP assays (Tina-quant hsCRP latex assay (validated to measure CRP concentrations between 0.3 – 20 mg) (Roche/Hitachi)). SuPAR and hsCRP have both proven stable in frozen samples (Riisbro et al. 2001, Nilsson et al. 2005).

SAFETY CONSIDERATIONS

There are no health-related risks for patients in relation to the blood analyses and outcome results. Due to the retrospective nature of the project it will not impose any burden on patients.

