### 2 DATA SOURCE

PATS: BMI, procedure codes, CPB time and aorta clamp time, procedure date, date and time for admission and discharge ICU.

ICCA: length of stay ICU (if missing in PATS)

Biochemical data: creatinine

The Danish National Patient Register: age, sex, date of death

Perfusionist charts: CPB time and aorta clamp time (if missing in PATS)

Sundhedsplatformen: type of surgery, previous PCI, AMI within 90 days of surgery, hypertension, diabetes mellitus, smoking status, left ventricle ejection fraction (LVEF), NYHA, CCS, date of discharge hospitalisation, length of stay ICU (if missing in PATS), and the following defined according to the EuroSCORE II; extracardiac arthropathy, mobility status, previous cardiac surgery, chronic lung disease, active endocarditis, critical preoperative state and pulmonary hypertension,

The blood samples for the study were drawn preoperatively or within the first 24 hours of surgery (only preoperative data for hsCRP included) and stored in the Persimune Biobank or two other biobanks at Dept. Cardiothoracic Anaesthesiology and Dept. Cardiothoracic Surgery, Rigshospitalet (registered [name], PhD and [name], respectively). The analysis is performed using commercially available analyses (suPARnostic® kit (validated to measure suPAR concentrations between 0.6 and 22 ng/mL) (ViroGates)). HsCRP will be measured by high sensitivity CRP assays (Tina-quant hsCRP latex assay (validated to measure CRP concentrations between 0.3 - 20 mg/L) (Roche/Hitachi)). In patients with CRP>20 mg/L a regular CRP-measurement will be performed.

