## 4 ANALYSIS SETS/ POPULATIONS/SUBGROUPS

The population includes adult patients ( $\geq$ 18 years) undergoing cardiac surgery at department of Cardiothoracic Surgery at Rigshospitalet, Copenhagen University hospital, Denmark.

Inclusion Criteria:

• Patients planned for elective on-pump cardiac surgery (isolated coronary artery bypass graft (CABG), single and multiple valvular procedures, combined CABG and valvular surgery, and others) and have given informed consent on delivering a blood sample for the biobank.

Exclusion Criteria:

• Peroperatively cancelling the surgery due to anatomic challenging findings, sudden change to offpump coronary artery bypass (OPCAB) surgery, death prior to surgery and project blood samples not available.

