### **5 ENDPOINTS AND COVARIATES**

### Primary objective

1. Association of preoperative suPAR values in relation to the censored time-to-event outcome "death from any cause" [Time Frame: from index surgery to date of data collection]

Secondary objectives:

- 2. Association of preoperative hsCRP values in relation to the censored time-to-event outcome "death from any cause" [Time Frame: from index surgery to date of data collection]
- 3. Assess whether adding suPAR, hsCRP or combined suPAR+hsCRP measurements improves predictive accuracy of EuroSCORE II [Time Frame: from index surgery to 30 days postoperative]
- 4. Sensitivity of the models; EuroSCORE II, suPAR, hsCRP, suPAR+hsCRP, EuroSCOREII+suPAR, EuroSCOREII+hsCRP and EuroSCOREII+suPAR+hsCRP in relation to the time-to-event outcome "death from any cause" [Time Frame: from index surgery to 30 days postoperative]
- 5. Specificity of the models; EuroSCORE II, suPAR, hsCRP, suPAR+hsCRP, EuroSCOREII+suPAR, EuroSCOREII+hsCRP and EuroSCOREII+suPAR+hsCRP in relation to the time-to-event outcome "death from any cause" [Time Frame: from index surgery to 30 days postoperative]
- 6. Asses association between suPAR and hsCRP measurements

Other outcome measures:

- 1. 30 days mortality measured by a yes/no question of "all-cause mortality" [Time Frame: from index surgery to 30 days]
- 2. 1-year mortality measured by a yes/no question of "all-cause mortality" [Time Frame: from index surgery to 1 year]

Covariates to be used in the analysis in order of priority according to number of events:

1. Sex (female/male), age (continuous), current smoker (status preoperative: yes/no), diabetes mellitus (status preoperative: yes/no), creatinine (preoperative: continuous), CPB time (continuous) and aorta clamp time (continuous), AMI within 90 days (status preoperative: yes/no)

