### 7.1 STATISTICAL PROCEDURES

A table 1 with patient characteristics for the entire study population will be generated presenting frequencies (percent), mean  $\pm$  standard deviation (SD), and median (25–75% quartile), where appropriate. This table will include the following variables: age (continuous (years)), sex (male), body-mass-index/BMI (continuous (kg/m^2), diabetes mellitus (NIDDM/IDDM), arterial hypertension (yes), EuroSCORE II value (continuous (%)), smoking status (never/previous/active), precious PCI (yes), NYHA (I-IV), CCS class 4 (yes), left ventricle ejection fraction/LVEF (continuous (%)), Previous cardiac surgery (yes), chronic lung disease (yes), acute myocardial infarction (AMI) within 90 days of surgery (yes), pulmonary hypertension (no, moderate, severe), weight on the intervention (isolated CABG, single non CABG, 2 procedures, 3 procedures), surgery on thoracic aorta (yes), baseline creatinine (continuous ( $\mu$ mol/L)), hsCRP (continuous (mg/L)), suPAR (continuous (ng/mL)),

In addition, the following peri- and postoperative variables will be used for analysis: cardiopulmonary bypass/CPB time (continuous (min)), aorta clamp time (continuous (min)), length of stay – ICU (continuous (hours)), length of stay – Hospitalisation (continuous (days)).

A table 2 will be generated including relevant tests for association between the individual variables mentioned above and continuous values of suPAR and hsCRP, respectively.

We will fit Cox proportional hazards models to assess the association between preoperative suPAR and hsCRPvalues and death from any cause. The goodness-of-fit of the Cox model will be investigated and the model will be adapted as required to fulfil the model assumptions. The model will be adjusted for sex, age, current smoker, AMI within 90 days, diabetes mellitus, creatinine, CPB time and aorta clamp time. 30-days survival will be modelled using logistic regression. If we cannot find Cox and/or logistic models that fit the data, alternative models will be considered.

Receiver operating characteristics (ROC) curve and area under the curve (AUC) analysis will be performed comparing EuroSCORE II, suPAR, hsCRP, suPAR+hsCRP, EuroSCOREII+suPAR, EuroSCOREII+hsCRP and EuroSCOREII+suPAR+hsCRP. Sensitivity and specificity values will be included.

Regression analysis between suPAR and hsCRP measurement will be performed.

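### Pairwise deletion with no common patient set lets the 30-day EuroSCORE II, suPAR and hsCRP models be compared in different patients

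*SAP*

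**What the plan says.** SAP section 6 sets the only missing-data rule in either document: "Missing values will be handled using pairwise deletion, still analysing all cases with the variable of interest". It gives the expected cause as follows: "Missing data is expected to be at random and due to device fault or misplaced registration". No expected rate is stated.

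SAP section 5 has as a secondary objective: "Assess whether adding suPAR, hsCRP or combined suPAR+hsCRP measurements improves predictive accuracy of EuroSCORE II", over 30 days. Sensitivity and specificity of the same models are two further secondary objectives. SAP section 7.1 plans ROC and AUC analysis "comparing EuroSCORE II, suPAR, hsCRP, suPAR+hsCRP, EuroSCOREII+suPAR, EuroSCOREII+hsCRP and EuroSCOREII+suPAR+hsCRP". The protocol's statistics section has the same list.

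SAP section 2 says that samples were "drawn preoperatively or within the first 24 hours of surgery (only preoperative data for hsCRP included"). The protocol's Methodology section sends tubes for about 1000 patients "from the respective biobank to the Dep. of Clinical Biochemistry for hsCRP analysis". SAP section 4, although its heading refers to analysis sets, gives eligibility criteria only. Its nearest approach to a completeness rule is the exclusion for "death prior to surgery and project blood samples not available".

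**The concern.** Whether a marker adds to EuroSCORE II is a within-patient question. A paired AUC test or a nested-model comparison needs the same patients in both models. Under the written rule, EuroSCORE II alone would use everyone with a EuroSCORE II value, while any model containing hsCRP would use only those with a preoperative hsCRP. The difference then mixes the marker's contribution with the effect of changing the patients.

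Deaths at 30 days are likely to be few, so losing one or two can move an AUC or a sensitivity visibly. At stake are the secondary objectives on added accuracy, sensitivity and specificity. The primary Cox analysis of suPAR is not affected by this point.

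**Working it through.** **Does any text supply a common set?** SAP section 4 lists eligibility. SAP section 7.1 and the protocol's statistics section list the seven models. None requires EuroSCORE II, suPAR and preoperative hsCRP in the same patient.

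**Is there a route to different sets?** Take a patient whose only sample was drawn after surgery. A project sample exists, so the exclusion for unavailable samples does not clearly remove this patient, but the hsCRP value is unusable.
- If the patient's suPAR is used, the suPAR and hsCRP models have different patients.
- If it is not used, EuroSCORE II alone still has more patients than the marker models.

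This loss comes from sample timing, which is not among the causes that SAP section 6 expects.

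**Inputs for the size.** The plan has no figure to reproduce. N = 951 is from the protocol title (the text says about 1000). The following are assumptions: AUC 0.75; 30-day mortality 2% (range 1–3%); hsCRP missing in 5% or 10%, with 1–2% as a low case. Scores are normal with equal spread in deaths and survivors, separated by √2 × z(0.75) = 1.414 × 0.674 = 0.954. The 0.02 threshold is illustrative; the documents set none.

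**Step 1: deaths.** 951 × 0.01 = 9.5; 951 × 0.02 = 19.0; 951 × 0.03 = 28.5. With 19 deaths, the chance that at least one leaves the hsCRP set is 1 − 0.95^19 = 0.62 at 5% missing and 1 − 0.90^19 = 0.865 at 10%. Each death carries 1/19 = 5.3 percentage points of sensitivity.

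**Step 2: one unchanged score, all patients against retained patients, random loss.** For missing fraction m, the SD of the difference is roughly SD(AUC) × √(m/(1 − m)). At 2% mortality SD(AUC) is 0.057:
- 5% missing: 0.057 × √(0.05/0.95) = 0.013
- 10% missing: 0.057 × √(0.10/0.90) = 0.019

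Simulation (20,000 replicates per mortality rate) agrees, with a mean difference of about 0:

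| Mortality | SD of one AUC | SD of difference, 5% missing | Over 0.02 | SD of difference, 10% missing | Over 0.02 |
|---|---|---|---|---|---|
| 1% | 0.083 | 0.021 | 17.9% | 0.031 | 32.1% |
| 2% | 0.057 | 0.014 | 12.4% | 0.020 | 25.6% |
| 3% | 0.047 | 0.011 | 7.4% | 0.016 | 17.8% |

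At 2% mortality with 1% or 2% missing, the SD is 0.006 or 0.008, and the difference exceeds 0.02 in about 2% or 4% of studies.

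**Step 3: a useless marker added by logistic refit.** Share of studies in which the apparent AUC change exceeds 0.02 in either direction (6,000 replicates per scenario; under 2% of replicates, at 1% mortality only, were dropped for too few deaths):

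| Mortality | 5% missing, common set | 5% missing, different sets | 10% missing, common set | 10% missing, different sets |
|---|---|---|---|---|
| 1% | 26.0% | 35.4% | 28.2% | 46.3% |
| 2% | 12.1% | 23.3% | 13.5% | 32.2% |
| 3% | 6.4% | 14.6% | 7.1% | 23.2% |

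At 2% mortality the mean gain is 0.0074 (common) against 0.0073 (different) at 5% missing, and 0.0079 against 0.0077 at 10%. A common set removes the extra spread but not the optimism from refitting.

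**Step 4: risk-linked loss.** If the top quarter of scores is lost 2 or 3 times as often, numerical integration at 2% mortality gives a systematic AUC shift of −0.0005 or −0.0008 at 5% missing, −0.0011 or −0.0020 at 10%, and −0.0044 or −0.0096 at an upper-bound 25%.

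**The case against.** The strongest case against is that the size is assumed throughout. The missing rate may be near zero, and at 1–2% missing the effect is slight. The exclusion for unavailable samples might be read as requiring a tube for each assay. SAP section 2 also rescues values above the hsCRP range with a regular CRP measurement. The objectives speak of preoperative suPAR; if that wording governs, patients sampled only after surgery lack both markers and the suPAR and hsCRP sets nearly coincide. Pairwise deletion could mean that each pair of models shares its patients, and no single results table is specified. Under random loss the effect is noise around zero, and nothing in the documents supports risk-linked loss. Imputation would keep every patient.

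Much of this limits the size, and it is accepted as such. It does not close the gap. A tube drawn after surgery is still an available sample. If suPAR must also be preoperative, EuroSCORE II alone keeps its surplus patients. The pair-sharing reading is not written, and if the seven models are reported side by side, one EuroSCORE II result cannot match every pair's patients. Imputation is a legitimate alternative, but the SAP does not plan it and it would need its own specification.

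**Conclusion.** The concern holds. The only written rule allows the 30-day models to be compared in different patients, and sample timing gives a concrete way for that to happen. Confidence in the textual gap is high; its practical effect depends on an unstated missing rate.

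The artefact is zero with complete data. In the central case (951 patients, 2% mortality, AUC 0.75, 5–10% missing at random) it adds an SD of 0.014–0.020 to an AUC difference, against a sampling SD of 0.057 for one AUC. It raises the chance that a useless marker appears to change the AUC by more than 0.02 from 12–14% to 23–32%. Systematic bias is at most about 0.002 at 10% missing, even with loss concentrated in high scores. This should be fixed because it is avoidable at little cost; it does not undermine the study.

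**What to change.** For the 30-day comparisons, replace pairwise deletion in SAP section 6 with wording such as:

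> All compared models are fitted and evaluated in the same patients. Set B (EuroSCORE II, suPAR and preoperative hsCRP all available) is used for the seven-model AUC, sensitivity and specificity results and for every comparison involving hsCRP. Set A (EuroSCORE II and suPAR available) is the primary set for EuroSCORE II versus EuroSCORE II+suPAR; the Set B result for that comparison is supportive. Number of patients, 30-day deaths and reasons for missing hsCRP are reported for each set.

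The SAP should also state whether suPAR from samples drawn after surgery is used, since that decides who belongs to each set.

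The cost is SAP wording and a few lines of code, with no new data. Set B loses some deaths: at 2% mortality and 10% missing, 951 × 0.02 × 0.10 = 1.9 of 19 under random loss. If the top quarter of scores is lost 2 or 3 times as often, the loss is 12.8% or 14.7% of 19.0, which is 2.4 or 2.8 deaths. Set A spares the suPAR comparison from losses due to missing hsCRP alone. The change does not address optimism from evaluating refitted models in the patients used to fit them.

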### 7 STATISTICAL METHODOLOGY

Protocol <Persimune\_suPAR\_study1> Statistical Analysis Plan

### 7.1 STATISTICAL PROCEDURES

A table 1 with patient characteristics for the entire study population will be generated presenting frequencies (percent), mean  $\pm$  standard deviation (SD), and median (25–75% quartile), where appropriate. This table will include the following variables: age (continuous (years)), sex (male), body-mass-index/BMI (continuous (kg/m^2), diabetes mellitus (NIDDM/IDDM), arterial hypertension (yes), EuroSCORE II value (continuous (%)), smoking status (never/previous/active), precious PCI (yes), NYHA (I-IV), CCS class 4 (yes), left ventricle ejection fraction/LVEF (continuous (%)), Previous cardiac surgery (yes), chronic lung disease (yes), acute myocardial infarction (AMI) within 90 days of surgery (yes), pulmonary hypertension (no, moderate, severe), weight on the intervention (isolated CABG, single non CABG, 2 procedures, 3 procedures), surgery on thoracic aorta (yes), baseline creatinine (continuous ( $\mu$ mol/L)), hsCRP (continuous (mg/L)), suPAR (continuous (ng/mL)),

In addition, the following peri- and postoperative variables will be used for analysis: cardiopulmonary bypass/CPB time (continuous (min)), aorta clamp time (continuous (min)), length of stay – ICU (continuous (hours)), length of stay – Hospitalisation (continuous (days)).

A table 2 will be generated including relevant tests for association between the individual variables mentioned above and continuous values of suPAR and hsCRP, respectively.

We will fit Cox proportional hazards models to assess the association between preoperative suPAR and hsCRPvalues and death from any cause. The goodness-of-fit of the Cox model will be investigated and the model will be adapted as required to fulfil the model assumptions. The model will be adjusted for sex, age, current smoker, AMI within 90 days, diabetes mellitus, creatinine, CPB time and aorta clamp time. 30-days survival will be modelled using logistic regression. If we cannot find Cox and/or logistic models that fit the data, alternative models will be considered.

Receiver operating characteristics (ROC) curve and area under the curve (AUC) analysis will be performed comparing EuroSCORE II, suPAR, hsCRP, suPAR+hsCRP, EuroSCOREII+suPAR, EuroSCOREII+hsCRP and EuroSCOREII+suPAR+hsCRP. Sensitivity and specificity values will be included.

Regression analysis between suPAR and hsCRP measurement will be performed.

Kaplan-Meier survival plots will be generated for the 4 quartiles of suPAR and hsCRP, respectively.

Two supplementary tables will be generated presenting the pre-, peri- and postoperative variables divided into the 4 quartiles of suPAR and hsCRP, respectively.

A two-sided *p* value <0.05 will be considered significant.

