Patients (≥ 18 years) undergoing elective on-pump cardiac surgery at the department of Cardiothoracic Surgery at Rigshospitalet, Denmark (isolated coronary artery bypass graft (CABG), single and multiple valvular procedures, combined CABG and valvular surgery, and others) and have given informed consent, is included. Exclusion criteria is; Perioperatively cancelling the surgery due to anatomic challenging findings, sudden change to off-pump coronary artery bypass (OPCAB) surgery, death prior to surgery and project blood samples not available.

Approximately 1000 patients will be enrolled in the biobank between 2012 and 2018 and will be included in the study. Data collection and analysis of the biomarkers is expected to be performed in 2019. The statistical analysis, writing of the manuscript and submission to a peer-reviewed journal is expected to be conducted in primo 2020. The study is approved by The Regional Committee on Health Research Ethics and the Data Protection Agency.

GENERAL INFORMATION

Protocol title: Predictive value of suPAR and hsCRP on postoperative mortality in 951 patients undergoing elective on-pump cardiac surgery.

Investigators:

Primary responsible:

[name] [name]
Rigshospitalet, University Hospital Copenhagen
Dept. Cardiothoracic Anaesthesiology
Copenhagen, Denmark

Senior responsible:

[name] [name], PhD, DMSc, Professor
Rigshospitalet, University Hospital Copenhagen
Dept. Cardiothoracic Anaesthesiology
Copenhagen, Denmark

[name] [name], PhD, Dept. Cardiothoracic Anaesthesiology, Rigshospitalet
[name], PhD, DMSc, Associate professor, Dept. Clinical Immunology, Rigshospitalet
[name], Ass. professor, Section of Biostatistics, University of Copenhagen.
[name], PhD, consultant, professor, centre director, the centre for cardiac, vascular, pulmonary and infectious diseases, Rigshospitalet

Collaborators:

PERSIMUNE, Department of Infectious Diseases, Rigshospitalet, Copenhagen University Hospital

The Department of Clinical Biochemistry, Rigshospitalet, Copenhagen University Hospital

Section of Biostatistics, University of Copenhagen.

RATIONALE & BACKGROUND INFORMATION

Hypothesis

We hypothesize that biomarkers reflecting a pro-inflammatory disease state at baseline; the soluble urokinase plasminogen activator receptor (suPAR) and high sensitivity C-reactive protein (hsCRP), can be used as preoperative predictors of outcome after cardiac surgery.

Aim

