This study aims to investigate whether preoperative soluble urokinase plasminogen activating receptor (suPAR) and High-sensitivity C-Reactive Protein (hsCRP) levels are associated with death from any cause during the study period following cardiac surgery. Further, to assess whether suPAR and hsCRP provides increased predictive accuracy of the clinical risk model EuroSCORE II, in predicting 30 days mortality. The purpose of the study is to gain knowledge on whether these inflammatory biomarkers might be able to reveal a pro-inflammatory disease state that represents a risk in patients undergoing cardiovascular surgery. Hence, these biomarkers may assist clinicians to gain more accurate risk identification and selecting compassionate treatment for high risk patients.

Background

The risk models currently used to predict outcome after cardiac surgery only explain a minor part of the observed variation in perioperative complications between patients. A recent trend in risk modelling has been the addition of various biomarkers to supplement clinical risk factors. By identifying predictive parameters of postoperative outcome such as biomarkers, future prevention- and treatment strategies for high risk patients may be developed and reduce morbidity and mortality after cardiac surgery. These are the first steps towards introducing personalized medicine on the patient level and improve cost utility.

One of the most important contributors to morbidity after cardiac surgery is the systemic inflammatory response syndrome (SIRS). All patients have an inflammatory response after cardiac surgery, but in about 30% of all patients it may lead to shock, vital organ failure, poor outcome and death (Laffey et al. 2002). The inflammation most likely plays a central role in the development of failure in all vital organs postoperatively (Laffey et al. 2002, Karkouti et al. 2009, Kertai et al. 2015). Further, patients with pro-inflammatory disease states preoperatively, such as coronary heart disease, heart failure and diabetes are at increased risk of SIRS and poor outcome after cardiac surgery.

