HsCRP has received a lot of attention regarding screening, reclassification and prediction of treatment response in patients suffering from cardiovascular disease, and elevated levels of hsCRP preoperatively was found to be associated with increased risk of postoperative cardiovascular events after on-pump coronary artery bypass grafting surgery (Yousuf et al. 2013, Balciunas et al. 2009). A Danish study from 2018 has revealed, that elevated suPAR and CRP were associated with cardiovascular risk and had predictive value among the 60-year old, and suPAR was of particular importance among women (Diedrichsen et al. 2018). Hence, these inflammatory biomarkers might be able to reveal a pro-inflammatory disease state that represents a risk in patients undergoing cardiovascular surgery, leading to a stronger inflammatory response with subsequent increased morbidity and mortality.

STUDY GOALS AND OBJECTIVES

The goals of this study are to assess how a high pro-inflammatory disease state at baseline reflected by the biomarkers suPAR and hsCRP, is associated with adverse outcome after cardiac surgery. We also expect that suPAR and/or hsCRP can provide increased predictive accuracy of the risk model EuroSCORE II which is currently being used for risk stratification in many hospitals.

Primary objective

1. Association of preoperative suPAR values in relation to the censored time-to-event outcome “death from any cause” [Time Frame: from index surgery to date of data collection]

Secondary objectives:

1. Association of preoperative hsCRP values in relation to the censored time-to-event outcome “death from any cause” [Time Frame: from index surgery to date of data collection]
2. Assess whether adding suPAR, hsCRP or combined suPAR+hsCRP measurements improves predictive accuracy of EuroSCORE II [Time Frame: from index surgery to 30 days postoperative]
3. Sensitivity of the models; EuroSCORE II, suPAR, hsCRP, suPAR+hsCRP, EuroSCOREII+suPAR, EuroSCOREII+hsCRP and EuroSCOREII+suPAR+hsCRP in relation to the time-to-event outcome “death from any cause” [Time Frame: from index surgery to 30 days postoperative]
4. Specificity of the models; EuroSCORE II, suPAR, hsCRP, suPAR+hsCRP, EuroSCOREII+suPAR, EuroSCOREII+hsCRP and EuroSCOREII+suPAR+hsCRP in relation to the time-to-event outcome “death from any cause” [Time Frame: from index surgery to 30 days postoperative]
5. Asses association between suPAR and hsCRP measurements

Other outcome measures:

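### The only adjusted Cox model for preoperative suPAR conditions on bypass and clamp time; a preoperative-covariate model, on preoperative samples, should be reported beside it

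*SAP*

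**What the plan says.** The Protocol's hypothesis is that the two markers "can be used as preoperative predictors of outcome after cardiac surgery". The primary objective, worded alike in the Protocol and SAP 5, is "Association of preoperative suPAR values in relation to the censored time-to-event outcome" of death from any cause, followed from surgery to data collection.

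One adjustment set is given, in the Protocol (Sample size and statistical analyses) and in SAP 7.1, and it serves both markers: "The model will be adjusted for sex, age, current smoker, AMI within 90 days, diabetes mellitus, creatinine, CPB time and aorta clamp time". SAP 5 repeats the eight covariates in an order of priority tied to the number of events, with both operative times ahead of AMI, which comes last.

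SAP 7.1 itself separates the operative times from the patient characteristics: "the following peri- and postoperative variables will be used for analysis: cardiopulmonary bypass/CPB time (continuous (min)), aorta clamp time". Among the patient characteristics it lists "left ventricle ejection fraction/LVEF (continuous" and "weight on the intervention (isolated CABG, single non CABG, 2 procedures, 3 procedures". Neither of these is in the Cox model or in the SAP 5 list.

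On sampling, Protocol Methodology and SAP 2 allow blood taken either before the operation or within 24 hours of it. The restriction to preoperative data is written for hsCRP only.

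**The concern.** The question is about risk identification before surgery. A hazard ratio that holds CPB and clamp time fixed compares patients with the same operative course, which nobody knows when the marker is measured. The set also has no measure of ventricular function, although the Protocol's Background names heart failure as a pro-inflammatory state with poor outcome, so the estimate may carry residual confounding by LVEF.

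This is the main estimate for the primary objective. With one model only, readers cannot see how far the suPAR hazard ratio depends on operative time or on LVEF, and they get no long-term estimate given preoperative facts alone. For a suPAR sample drawn after bypass, operative time comes before the marker, so the same covariate plays a different role in different patients.

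**Working it through.** **1. Is the gap filled elsewhere?** The plan states no death count, hazard ratio or power, so there is no figure to reproduce. The other analyses are:

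- Freedom to change the Cox model ("the model will be adapted as required to fulfil the model assumptions") is tied to fit and assumptions, not to the question asked.
- Table 2 tests each variable against suPAR one at a time; it does not show the effect on the hazard ratio.
- Kaplan-Meier curves by quartile are unadjusted.
- The 30-day logistic model has no named covariates.
- EuroSCORE II with the markers is assessed to 30 days only.

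None gives a long-term hazard ratio conditional on preoperative covariates.

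**2. Possible size, by formula.** All inputs are assumed.

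- Omitted LVEF multiplies the HR per SD of suPAR by about exp(r × b), where r is the correlation of suPAR with poorer LVEF and b the log-hazard per SD of poorer LVEF. With r from 0.05 to 0.20 and b from 0.2 to 0.4: exp(0.01) to exp(0.08) = 1.01 to 1.08.
- If operative time is a mediator, conditioning on it multiplies the HR by about exp(−a × m), where a is the link from suPAR to operative time and m its log-hazard. On the same ranges: exp(−0.08) to exp(−0.01) = 0.92 to 0.99.
- Net: exp(0.01 − 0.08) = 0.93 to exp(0.08 − 0.01) = 1.07. With three values per input there are 81 combinations: 34 above 1, 34 below, 13 equal to 1. The symmetry comes from using equal ranges, so it says nothing about the true direction.

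Taking 5, 10 or 15% deaths among 951 patients gives 48, 95 or 143 deaths. The best-case SE of the log HR, 1/√deaths, is 0.144, 0.103 or 0.084. The largest net shift, 0.07, is then 0.48, 0.68 or 0.84 of one SE.

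These limits depend on r ≤ 0.20. With r = 0.3 and HR 1.4 per SD of LVEF, and no offset from operative time, the factor is exp(0.3 × ln 1.4) = exp(0.101) = 1.11, or 0.70, 0.98 and 1.21 SE.

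**3. Simulation.** 100,000 patients per scenario, 12% deaths, direct suPAR HR 1.30 per SD. LVEF, where active, has HR 1.4 per SD. Operative time depends on procedure type, with HR 1.5 per unit of its score. The preoperative model holds procedure type (4 levels) and LVEF.

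| suPAR effect on time | suPAR-LVEF correlation | Planned-type HR | Preoperative HR |
|---|---|---|---|
| 0 | 0 (LVEF inactive) | 1.31 | 1.30 |
| 0.2 | 0 (LVEF inactive) | 1.30 | 1.41 |
| 0 | 0.15 | 1.38 | 1.31 |
| 0 | 0.3 | 1.44 | 1.30 |
| 0.2 | 0.15 | 1.35 | 1.40 |
| 0.2 | 0.3 | 1.44 | 1.41 |

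A second simulation (10 runs of 20,000, 10% deaths) treated operative time purely as a proxy for procedural complexity. Replacing it by weight of the intervention changed the HR by −0.3% to +1.9%; dropping it with no procedure term raised the HR by about 3.5%. A preoperative model therefore needs a procedure term.

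**4. Can two fits be told apart?** On the same patients, yes. In the second simulation the Monte Carlo SE of the log ratio of the two HRs was 0.0016 over 10 runs of 2,000 deaths. Scaled to 95 deaths: 0.0016 × √10 × √(2000/95) = 0.023, against 0.103 for one log HR.

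**5. Model size** (one marker, linear).

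| Model | Parameters | Deaths per parameter at 48 / 95 / 143 |
|---|---|---|
| Planned | 1 + 8 = 9 | 5.3 / 10.6 / 15.9 |
| Preoperative, weight 3 df | 1 + 6 + 3 = 10 | 4.8 / 9.5 / 14.3 |
| The same plus LVEF | 11 | 4.4 / 8.6 / 13.0 |
| Preoperative, weight 1 df | 8 | 6.0 / 11.9 / 17.9 |

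**6. Loss of post-surgery suPAR samples.** The share is not stated. If 10, 30 or 50% are lost, the SE rises by 1/√0.9 = 1.05, 1/√0.7 = 1.20 or 1/√0.5 = 1.41. At 30%, 95 deaths become about 67, or 8.3 per parameter with weight as 1 df.

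**The case against.** The strongest reply is that the objective is an association, and that adjusting for operative course answers a proper question. That stands. A reader might infer that including CPB and clamp time is over-adjustment that pulls the suPAR effect towards no effect, so the set must be replaced. The documents do not support this: nowhere do they say that suPAR acts through operative time. The two times may stand in for procedural complexity, and they are the only procedure-related terms in the model.

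A reader might also infer that omitting LVEF inflates the result. That is equally unproven. LVEF may be a confounder, or part of what the study wants the marker to show, namely "whether these inflammatory biomarkers might be able to reveal a pro-inflammatory disease state that represents a risk".

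Three further points stand. The illustrated shifts rest on assumed inputs and are mostly below one SE. No section says whether weight of the intervention is coded as planned or as performed; its place in the patient-characteristics list does not settle that. Collapsing weight to 1 df still needs 80 deaths to reach 10 per parameter, so it guarantees nothing.

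The objection does not remove the gap. Table 2 and the quartile tables will show how suPAR relates to LVEF and operative time, but not what that does to the hazard ratio.

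**Conclusion.** The point holds as a mismatch between question and model, not as an error in the planned model. The planned hazard ratio is the association given operative course; the plan has no long-term association given preoperative facts, although it collects the data for one. The sampling rule for suPAR also conflicts with the primary objective's restriction to preoperative values, and those sections must be reconciled.

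Size and direction are unknown. On the assumed ranges the net factor is about 0.93 to 1.07, under one SE at 48 to 143 deaths; only a stronger assumed link between suPAR and LVEF takes it past that. The issue is therefore more what the hazard ratio means than how large it is. This is a cheap improvement and does not justify discarding the planned set.

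**What to change.** Amend the Protocol (Methodology; Sample size and statistical analyses) and SAP 2, 5, 6 and 7.1 together.

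1. Base the suPAR analysis of the primary objective on samples drawn before surgery, as for hsCRP. Report all suPAR samples as a sensitivity analysis.
2. For both suPAR and hsCRP, prespecify a preoperative Cox model with age, sex, current smoking, diabetes, AMI within 90 days, creatinine and weight of the intervention, without CPB and clamp time. Report it beside the planned model on the same patients. State whether weight is coded as planned or as performed.
3. Report that model again with continuous LVEF, noting that LVEF may be a confounder or part of the disease state. State how missing LVEF is handled, since SAP 6 offers only pairwise deletion, which can put different patients in different fits. Give patients and deaths for each fit.
4. Rest conclusions about preoperative risk identification on the preoperative model, and label the model with CPB and clamp time as the association given operative course.
5. If deaths are few, reduce weight to isolated CABG versus other (1 df) and state deaths per parameter, without claiming that this secures 10.

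Cost: a few extra fits; 10 or 11 parameters against 9; the timing of each suPAR sample must be retrievable, and the documents do not list it among the collected data. Some precision is lost if samples were drawn after surgery. The hazard ratio may turn out less favourable, and weight may capture complexity less fully than operative time, which the side-by-side report would show.
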